View	Data Collection Spreadsheet	Weighted Blanket Data Spreadsheet 5 23 2023.xlsx	0.01	5/23/2023 11:02 AM	[name]	Other	Yes
View	Patient Participant Experience Survey	Weighted Blanket Participant Survey 5 23 2023.pdf	0.01	5/23/2023 11:02 AM	[name]	Research Measure	Yes
View	Legally Authorized Representative (LAR) Experience Survey	Weighted Blanket Legally Authorized Representative Survey 05 23 2023.pdf	0.01	5/23/2023 11:02 AM	[name]	Research Measure	Yes
View	Healthcare Provider Perception of Participant Experience Survey	Weighted Blanket Healthcare Provider Perception of Participant Survey 05 23 2023.pdf	0.01	5/23/2023 11:01 AM	[name]	Research Measure	Yes
View	Healthcare Provider Experience Survey	Weighted Blanket Healthcare Provider Experience Survey 05 23 2023.pdf	0.01	5/23/2023 11:01 AM	[name]	Research Measure	Yes
View	PROC Approval Letter	VCU ONETRAC Notifier - PROC Request #397 - Approval Without Revision.pdf	0.01	5/21/2023 10:26 PM	[name]	Other	Not Applicable

Document Name	Document	Version	Date Modified	Uploaded By	Type	Approved	
View	[name] Biosketch	Weighted Blanket [name] Biosketch Wright Center Rural Pilot.docx	0.01	5/21/2023 10:17 PM	[name]	CV/Biosketch	Not Applicable

ID: MS12_HM20027241

View: SF2 - Documents Complete

Documents Complete

Protocol Progress:

- ? INITIAL SETUP
- ? BACKGROUND, RATIONALE & GOALS
- ? RESEARCH PLAN
- ? CONSENT PLAN
- ? RISKS, PRIVACY & CONFIDENTIALITY
- ? POPULATIONS WITH SPECIAL CONSIDERATIONS
- ? INSTITUTIONAL REQUIREMENTS
- ? DOCUMENTS

End of Application

Click Continue below to exit and submit this project

ID: MS12_HM20027241

View: Copy of Bio-Med Devices

Bio-Medical Devices

1. * **Name:**
Weighted Blanket
2. * **Manufacturer:**
Sensory Goods
3. * **What risk has the sponsor or sponsor-investigator designated the device:**
Non-Significant Risk
4. * **Indicate the device's IDE number if a protocol was submitted to the FDA for any investigational device or new use of a marketed device (regardless of what the FDA's determination was).**

Or, if a protocol was not submitted to the FDA:

- Enter "Abbreviated IDE" if the sponsor or sponsor-investigator has designated the device as a Non-Significant Risk device
- Enter "IDE Exempt" if the sponsor or sponsor-investigator has determined that the device qualifies for IDE exemption
- Enter "Regulatory Discretion" for a mobile application with regulatory discretion
- Enter the FDA-provided HDE number if a HUD is being used in a clinical investigation for the HDE-approved indication(s).

Abbreviated IDE

5. * **Select who holds the Investigational Device Exemption (FDA-granted IDE or Abbreviated IDE) for the device:**

External to VCU Sponsor or Investigator

VCU Sponsor-Investigator

VCU Sponsor who is not the Investigator

Not Required

6. **If someone other than the PI is the sponsor for the IDE, name the entity or individual who will be the IDE sponsor.**

ID: MS12_HM20027241

View: SF_IRB_Summary_Document

Add Document

1. * **Document Name:**
Version 3_Weight Blanket Study Consent Form_5-23-2024_Clean.docx
2. * **Type:**
Consent/Assent/Information Sheet
3. * **File:**
 Version 3_Weight Blanket Study Consent Form_5-23-2024_Clean.pdf(0.03)

Add Document

- * Document Name:**
Version 3_Weight Blanket Study Consent Form_5-22-2024_Redlined.docx
- * Type:**
Consent/Assent/Information Sheet
- * File:**
 Version 3_Weight Blanket Study Consent Form_5-22-2024_Redlined.docx(0.01)

Add Document

- * Document Name:**
Consent Form
- * Type:**
Consent/Assent/Information Sheet
- * File:**
 Weight Blanket Study Consent Form_10-11- 2023 - Copy - Copy.pdf(0.04)

Add Document

- * Document Name:**
Weighted Blanket Device Information
- * Type:**
Other
- * File:**
 Weighted Blanket Info for IRB_07 27 2023.docx(0.02)

Add Document

- * Document Name:**
Data Collection Spreadsheet
- * Type:**
Other
- * File:**
 Weighted Blanket Data Spreadsheet 5 23 2023.xlsx(0.01)

Add Document

- * Document Name:**
Patient Participant Experience Survey
- * Type:**
Research Measure
- * File:**
 Weighted Blanket Participant Survey 5 23 2023.pdf(0.01)

Add Document

1. * **Document Name:**
Legally Authorized Representative (LAR) Experience Survey
2. * **Type:**
Research Measure
3. * **File:**
 [Weighted Blanket Legally Authorized Representative Survey 05 23 2023.pdf\(0.01\)](#)

Add Document

1. * **Document Name:**
Healthcare Provider Perception of Participant Experience Survey
2. * **Type:**
Research Measure
3. * **File:**
 [Weighted Blanket Healthcare Provider Perception of Participant Survey 05 23 2023.pdf\(0.01\)](#)

Add Document

1. * **Document Name:**
Healthcare Provider Experience Survey
2. * **Type:**
Research Measure
3. * **File:**
 [Weighted Blanket Healthcare Provider Experience Survey 05 23 2023.pdf\(0.01\)](#)

Add Document

1. * **Document Name:**
PROC Approval Letter
2. * **Type:**
Other
3. * **File:**
 [VCU ONETRAC Notifier - PROC Request #397 - Approval Without Revision.pdf\(0.01\)](#)

Add Document

1. * **Document Name:**
[name] Biosketch
2. * **Type:**
CV/Biosketch

Consent Groups

1. * Enter a descriptive name for this consent / assent group:
Patient Participant

2. * Select all that apply to this consent / assent group:

Name
 Signed Consent by Participant
 Signed Parent/Guardian Permission or Legally Authorized Representative Consent
 Signed Assent by Child or Decisionally Impaired Adult
 Verbal/Other Indication of Assent by Child or Decisionally Impaired Adult
 Short Form Consent (limited applicability)
 None of the Above (select waiver below)

3. * Select all electronic signature platforms that apply to this consent / assent group:

 Not using electronic signature platforms
 DocuSign Part 11 (FDA regulated studies)
 DocuSign (standard platform for non-FDA regulated studies)
 REDCap e-Consent
 iMedConsent (Veterans Affairs studies)
 Other electronic signature platform

4. If Other is selected, explain:

5. * Select any waivers that apply to this consent / assent group:

 No Waivers Requested
 Waiver of All Consent or Some Elements in Consent Form
 Waiver of Parental Permission or Legally Authorized Representative Consent
 Waiver of All Assent by Child or Decisionally Impaired Adult
 Waiver of Signature on Consent/Permission Forms (waiver of documentation of consent)
 Exception from Informed Consent (for emergency research only)

6. * Select all study team role(s) that will obtain consent / assent from this group:

 Principal Investigator
 Co/Sub-Investigator
 Medical or Psychological Responsible Investigator
 Lead Student/Trainee Investigator (leading their own project)
 Research Coordinator
 Research Nurse
 Consultant
 Research Assistant
 Pharmacist
 Statistician

- Regulatory Coordinator

- Trainee/Student(working on project)

- Other

- N/A: Requesting Waiver of Consent

7. * Describe the consent procedures used for this group. Address each point below:

- **When and where consent will occur**
- **What will be covered during the consent discussion**
- **How the consent discussion will occur (e.g. in-person, phone, video conference)**
- **How you will reconfirm consent on an ongoing basis, if applicable**

At the VCU Health Medical Center Main Hospital, the informed consent process will occur in an in-patient (bedside or unoccupied family conference room) or telephone setting. If the patient is decisionally competent (alert and oriented), the patient will be approached. If the patient is decisionally impaired in any capacity, the legally authorized representative (LAR) will be approached for consent. In that case, the patient will give a signed, verbal, or other indication of assent, if possible. During the informed consent process, an unbiased review of the trial and consent form will be discussed. It will be stated that the patient will continue to receive standard of care, with or without consenting for the voluntary trial. A physical copy of a consent form will be used. If the LAR is not available in person, the consent discussion may occur via telephone.

At the VCU Health Community Memorial Hospital, consent will in the same manner as it will at the VCU Medical center but all in-person activities will occur using remote technology (i.e., Zoom). A designated study team member at the CMH site will provide the patient and/or their LAR a study-specific iPad so that the study team member conducting the ICF process can speak with them using live communication via Zoom. The CMH team member will provide the patient and/or LAR a physical copy of the ICF to review during the discussion. If the patient and/or LAR agree to enroll the patient, they will sign the form and will give it to the CMH study team member who will place it in a locked cabinet at CMH dedicated for the study until it is transported by the study PI or Co-I to the study office at VCU Medical Center.

8. * Select the processes for minimizing any potential perception of undue influence to participate, particularly when there is a pre-existing relationship between the participant and the researcher (e.g. treatment provider/patient; instructor/student; supervisor/employee, etc.):

- Having a 3rd person (family/friends, another study team member, etc.) present during the consent / assent discussion
- Having an independent advocate (e.g. advocate for decisionally impaired adults, wards) present during the consent / assent discussion
- Removing physical symbols of authority like white coats or police badges
- Sitting down beside the participant instead of standing over them
- If obtaining consent / assent in a clinical setting, letting patients sit instead of lie down (if they are able to)
- Moving to a more neutral location like a conference room
- Obtaining consent / assent after other services/interactions have been completed (e.g. after school or the clinic visit)
- Having a mandatory wait period for the participant to go home and think before they sign consent /assent
- Sharing the consent / assent discussion between two people (i.e. a clinician might be the best person to explain study procedures and risks, but then they could step out and let a research assistant finish the consent process)
- Other protection(s) not listed here describe below
- N/A: Requesting Waiver of Consent

9. * Describe the other ways the study team will minimize any potential perception of undue influence to participate:

The study team will emphasize that the trial is voluntary and standard of care will be performed with or without consenting.

10. * How much time will participants be given to make a decision:

The patient and/or their LAR will be given as much time as possible to make a decision, as long as it is within the indicated 72 hour time frame.

11. If applicable, describe the procedures for consenting children upon entering adulthood or participants who are no longer decisionally impaired:

Continual assent will be sought for any patient enrolled that is decisionally impaired. This will enable the team to ensure their assent if they become no longer decisionally impaired.

Consent Groups

1. * Enter a descriptive name for this consent / assent group:

Healthcare Provider

2. * Select all that apply to this consent / assent group:

Name

- Signed Consent by Participant

- Signed Parent/Guardian Permission or Legally Authorized Representative Consent

- Signed Assent by Child or Decisionally Impaired Adult

Name Verbal/Other Indication of Assent by Child or Decisionally Impaired Adult Short Form Consent (limited applicability) **None of the Above (select waiver below)****3. * Select all electronic signature platforms that apply to this consent / assent group:** **Not using electronic signature platforms** DocuSign Part 11 (FDA regulated studies) DocuSign (standard platform for non-FDA regulated studies) REDCap e-Consent iMedConsent (Veterans Affairs studies) Other electronic signature platform**4. If Other is selected, explain:****5. * Select any waivers that apply to this consent / assent group:** No Waivers Requested **Waiver of All Consent or Some Elements in Consent Form** Waiver of Parental Permission or Legally Authorized Representative Consent Waiver of All Assent by Child or Decisionally Impaired Adult Waiver of Signature on Consent/Permission Forms (waiver of documentation of consent) Exception from Informed Consent (for emergency research only)**6. * Select all study team role(s) that will obtain consent / assent from this group:** Principal Investigator Co/Sub-Investigator Medical or Psychological Responsible Investigator Lead Student/Trainee Investigator (leading their own project) Research Coordinator Research Nurse Consultant Research Assistant Pharmacist Statistician Regulatory Coordinator Trainee/Student(working on project) Other **N/A: Requesting Waiver of Consent****7. * Describe the consent procedures used for this group. Address each point below:**

- When and where consent will occur
- What will be covered during the consent discussion
- How the consent discussion will occur (e.g. in-person, phone, video conference)
- How you will reconfirm consent on an ongoing basis, if applicable

At the end of the patient's participation (withdrawn or removed from ICU level of care), the healthcare provider (nurse, physicians, and/or APPs) will be asked to partake in a study survey with which we are asking for a waiver of consent. The survey will contain directions that specify that the survey is voluntary and that the answers provided will not be identifiable to others in any way. An iPad will be brought to the healthcare provider by a member of the study team with the healthcare provider survey opened. After reading the directions, the healthcare provider's decision to complete their survey will indicate their consent to participate. This activity will only be done in person using a study-specific iPad.

8. * Select the processes for minimizing any potential perception of undue influence to participate, particularly when there is a pre-existing relationship between the participant and the researcher (e.g. treatment provider/patient; instructor/student; supervisor/employee, etc.):

- Having a 3rd person (family/friends, another study team member, etc.) present during the consent / assent discussion
- Having an independent advocate (e.g. advocate for decisionally impaired adults, wards) present during the consent / assent discussion
- Removing physical symbols of authority like white coats or police badges
- Sitting down beside the participant instead of standing over them
- If obtaining consent / assent in a clinical setting, letting patients sit instead of lie down (if they are able to)
- Moving to a more neutral location like a conference room
- Obtaining consent / assent after other services/interactions have been completed (e.g. after school or the clinic visit)
- Having a mandatory wait period for the participant to go home and think before they sign consent /assent
- Sharing the consent / assent discussion between two people (i.e. a clinician might be the best person to explain study procedures and risks, but then they could step out and let a research assistant finish the consent process)
- Other protection(s) not listed here describe below
- N/A: Requesting Waiver of Consent**

9. * Describe the other ways the study team will minimize any potential perception of undue influence to participate:

The study team will emphasize that the completion of the survey is voluntary and will in no way affect care of the patient enrolled in the study. The study team member will remain close by to ensure only the intended recipient receives the survey. However, they will be sure to not hover and allow the healthcare provider as much time as needed to complete the survey.

10. * How much time will participants be given to make a decision:

Once the healthcare provider is provided the survey and they have a chance to read the instructions, they will immediately be asked to complete the survey or return the iPad to the study team member without completing the survey.

11. If applicable, describe the procedures for consenting children upon entering adulthood or participants who are no longer decisionally impaired:

ID: MS12_HM20027241

View: SF_IRB_ConsentPlan_Groups

Consent Groups

1. * Enter a descriptive name for this consent / assent group:

Legally Authorized Representative (LAR)

2. * Select all that apply to this consent / assent group:

- | Name |
|---|
|  Signed Consent by Participant |
|  Signed Parent/Guardian Permission or Legally Authorized Representative Consent |
|  Signed Assent by Child or Decisionally Impaired Adult |
|  Verbal/Other Indication of Assent by Child or Decisionally Impaired Adult |
|  Short Form Consent (limited applicability) |
|  None of the Above (select waiver below) |

3. * Select all electronic signature platforms that apply to this consent / assent group:

- Not using electronic signature platforms**
- DocuSign Part 11 (FDA regulated studies)
- DocuSign (standard platform for non-FDA regulated studies)
- REDCap e-Consent
- iMedConsent (Veterans Affairs studies)
- Other electronic signature platform

4. If Other is selected, explain:

5. * Select any waivers that apply to this consent / assent group:

- | |
|---|
|  No Waivers Requested |
|  Waiver of All Consent or Some Elements in Consent Form |
|  Waiver of Parental Permission or Legally Authorized Representative Consent |
|  Waiver of All Assent by Child or Decisionally Impaired Adult |

Waiver of Signature on Consent/Permission Forms (waiver of documentation of consent)

Exception from Informed Consent (for emergency research only)

6. * Select all study team role(s) that will obtain consent / assent from this group:

Principal Investigator

Co/Sub-Investigator

Medical or Psychological Responsible Investigator

Lead Student/Trainee Investigator (leading their own project)

Research Coordinator

Research Nurse

Consultant

Research Assistant

Pharmacist

Statistician

Regulatory Coordinator

Trainee/Student(working on project)

Other

N/A: Requesting Waiver of Consent

7. * Describe the consent procedures used for this group. Address each point below:

- When and where consent will occur
- What will be covered during the consent discussion
- How the consent discussion will occur (e.g. in-person, phone, video conference)
- How you will reconfirm consent on an ongoing basis, if applicable

At the end of the patient's participation (withdrawn or removed from ICU level of care), the LAR will be asked to partake in a study survey with which we are asking for a waiver of consent. The survey will contain directions that specify that the survey is voluntary and that the answers provided will not be identifiable to others in any way. An iPad will be brought to the LAR by a member of the study team with the LAR survey opened. After reading the directions, the LAR's decision to complete their survey will indicate their consent to participate. This activity will only be done in person using a study-specific iPad.

8. * Select the processes for minimizing any potential perception of undue influence to participate, particularly when there is a pre-existing relationship between the participant and the researcher (e.g. treatment provider/patient; instructor/student; supervisor/employee, etc.):

- Having a 3rd person (family/friends, another study team member, etc.) present during the consent / assent discussion
- Having an independent advocate (e.g. advocate for decisionally impaired adults, wards) present during the consent / assent discussion
- Removing physical symbols of authority like white coats or police badges
- Sitting down beside the participant instead of standing over them
- If obtaining consent / assent in a clinical setting, letting patients sit instead of lie down (if they are able to)
- Moving to a more neutral location like a conference room
- Obtaining consent / assent after other services/interactions have been completed (e.g. after school or the clinic visit)

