Once informed consent is obtained, medical-grade weighted blankets (equal to approximately 10% of the participants body weight up to 20lbs maximum) will be applied to participants by the bedside nurse for a minimum of 6 continuous hours nightly between 7pm-7am and additional hours as desired by the patient, their LAR, or the patient's clinical care team. Weighted blankets of various weights will be readily available on the nursing unit; the study team will communicate with the bedside nurse regarding what weight blanket will be used for each patient enrolled. Hourly rounding by a study champion will be utilized to document blanket use between the hours of 7pm-7am. Participants will remain enrolled in the study until they are withdrawn (either at participant request, administrative due to an adverse event, or at the request of the clinical team), or they are transferred from an ICU level of care. Data will be collected on: (1) feasibility and acceptability of weighted blankets; (2) feasibility and acceptability of technology to promote rural participation; (3) preliminary descriptive data and trends related to delirium, agitation, ventilator days, length of stay; and (4) participant demographics (see Data Collection Spreadsheet supporting document attached). A REDCap database the incorporates all data points needed to answer study aims will be developed with the assistance from the Wright Center Biostatistical Consulting Laboratory. Data analysis will include descriptive statistics and comparison statistics between VCUMC and CMH. Once the patient's participation ends (withdrawn or transferred from an ICU level of care), the patient (if alert and oriented), the patient's LAR, the patient's nurse, and the patient's physicians and/or advanced practice providers (APPs) will be asked to complete an electronic survey based on their experience with the weighted blanket use. Surveys will only be administered if a patient uses the blanket for at least one night. The survey will be in REDCap; no participant identifiers will be used. The survey will be opened by a member of the study team and brought to the participant on a study dedicated iPad. The study team member will remain in close proximity until the participant indicates they are done. At the time, the study team member will collect the iPad and ensure the survey has been closed. Who the patient's nurse and physicians/APPs are for the day will be determined by the ICU's electronic assignment board and/or care team noted in the EHR via the storyboard.

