The inclusion criteria for each patient participant will be verified via medical record screening. In the inclusion criteria, it is stated that each participant must be 18 years of age or older. The waiver of consent language at the top of the healthcare provider and LAR survey will enforce the need for the respondent to be 18 years of age or older. By proceeding through the survey, they are self-verifying that they meet the age criteria.

ID: MS12_HM20027241

View: SF2 - Secondary Data/Specimen Details

Secondary Data/Specimen Details

1. * Describe the source(s) and nature of the information/specimens being obtained. This response should:

- Identify where the data/specimens will come from (e.g., another researcher's registry, pathology lab, commercial source, medical records, etc.); and
- List what types of specimens will be obtained (when applicable); and/or
- List all data elements that will be obtained (when applicable). A data collection form or other documentation may be uploaded and referenced here.

a. Data will be collected from the participants electronic health record (EHR)

b. No specimens will be collected during this study.

c. See attached Data Collection Spreadsheet document which contains all information that will be obtained from the EHR (demographic, delirium/agitation assessments, sedation/pain medications, diagnoses, history, hospital history, ventilator use, etc.)

2. * Describe whether any agreement exists between you and data/specimen provider that states you will never have access to the ability to identify the participants (i.e. access to identifiers or the code key) and that you will not attempt to re-identify individuals.

We will be assigning participants sequential study IDs that will be kept secure and separate from patient identifiers. The study team are clinical providers within VCU Health. Once a patient has been removed from the study and data collection has been completed, we will not attempt to re-identify individuals.

3. * When the information/specimens were originally collected, did individuals provide consent for secondary research use of their data/specimens (i.e. consent to another research study or to a research registry)?

Yes

No

ID: MS12_HM20027241

View: SF2 - Costs to Participants

Costs to Participants

1. * Select all categories of costs that participants or their insurance companies will be responsible for:

- Participants will have no costs associated with this study

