Physical risk: The addition of a weighted blanket increases the amount of pressure placed on a patient's skin. Additionally, the weight of the blanket itself increases the risk of injury for the nurse applying the blanket to the patient each night (related to lifting of blanket).

Research data risk: There is a risk of loss of confidentiality and privacy for data collected from the patient's EHR record.

2. * Describe how each of the risks/harms/discomforts identified above will be minimized:

The minimize the physical risk for patients, exclusion criteria have been designed to eliminate enrollment of those with skin breakdown, or risk thereof.

The design of the study includes no additional safeguards for the nurses moving the weighted blankets. However, the weight of the blankets does not exceed lifting requirements of unit nurses. Additionally, proper body mechanics are fundamental to nursing education received by all nurses.

To minimize the risk of loss of confidentiality and privacy, only study team members will have access to the data collected. Additionally, data collected will be stored in REDCap, a secure system endorsed by VCU. Only aggregated, de-identified data will be used for reporting purposes.

3. * Describe any potential risks or harms to a community or a specific population based on study findings (e.g. information that could be stigmatizing or derogatory):

Not applicable.

4. Where appropriate, discuss provisions for ensuring necessary medical, professional, or psychological intervention in the event of adverse events to the subjects:

Although unlikely, any skin injury as a result of weighted blanket use would be medically treated as all other developing skin injuries. Additionally, use of the weighted blanket would immediately cease.

5. * Describe criteria for when the investigator would withdraw an individual participant from the study; such as safety or toxicity concerns, emotional distress, inability to comply with the protocol, etc.:

The investigator would withdrawal an individual participant from the study if any skin changes are noted on daily physical examinations, the patient experiences increased agitation with blanket use as reported by the patient's nurse, or the patient displays a lack of assent over blanket use.

6. * Summarize any pre-specified criteria that would trigger the investigator/sponsor/monitoring committee to stop or change the study protocol due to safety concerns:

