The investigator will re-examine the study protocol if any adverse events occur. Adverse events are based on the risks identified above (patient skin injury or increased agitation, nurse lifting-related injury, loss of participant confidentiality or privacy).

Data and Safety Monitoring

Data and safety monitoring is a system for checking the studys data at regular intervals over the study period to identify and address issues that could affect the safety of research participants. This requirement is in accordance with 45 CFR 46.111.

The purpose of data and safety monitoring plan is to set forth study team procedures for monitoring/addressing:

- Participant safety (physical, psychological, etc.)
- Data validity
- Early stopping (termination) based upon changes in risks and benefits.

7. * Indicate if this study will have a Data Safety Monitoring Board (DSMB) or a Data Safety Monitoring Plan (DSMP): [Required for all greater than minimal risk studies]

- DSMB
- DSMP
- No DSMB/DSMP [Note: This response is not applicable for greater than minimal risk studies]**

ID: MS12_HM20027241

View: SF2 - Privacy

Privacy

Privacy refers to an individual's right to control how others view, record, or obtain information about them. When privacy is violated it can involve such things as

- Being asked personal questions in a public setting;
- Being publicly identified as having a particular characteristic or diagnosis;
- Being seen entering a place that might be stigmatizing;
- Being photographed, videotaped or observed without consent;
- Disclosure of personal information to unauthorized people

Privacy is not the same as confidentiality because privacy protections apply to people, and confidentiality protections apply to data. Confidentiality protections should be described on the Data Confidentiality page of this form, not here.

Instructions for this page:

Select all the applicable ways that the research team will protect participants' privacy throughout the course of the study. **The options listed include some of the most common best practices. Not all will be applicable to every study.**

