The following health information will be collected from the participant's medical record while enrolled in the study: Participant medical history/diagnoses, admission diagnoses, agitation and delirium scores, sedation and pain medications given and amounts given, hospital length of stay, ICU length of stay, and number of days ventilated.

3. * Describe the source(s) of the protected health information (e.g. Informatics or which clinical databases):
The source of the PHI will be demographic and clinical data entered into the participant's EHR (Epic)
4. * Does the PI certify that this study's access to and use of the protected health information is limited to the minimum amount necessary to be able to effectively conduct the research?
 Yes No
5. * Select all pathways this research will employ to use or access PHI (selections will branch):
- De-Identified Data (none of the 18 identifiers are recorded or associated with the research data)
 - Limited Data Set
 - Waiver of Authorization
 - Partial Waiver of Authorization (temporary waiver for recruitment purposes and/or waiver of some elements of Authorization)
 - Signed Authorization Combined with Consent Form
 - Signed Authorization as Stand-Alone Form

ID: MS12_HM20027241

View: SF2 - Partial Waiver of Authorization

Partial Waiver of Authorization

1. * Select the purpose for requesting the partial waiver of authorization:
- Identify possible participants to recruit for the study
 - Waive some elements of authorization (such as signature)
2. * Explain how the partial waiver of authorization poses no greater than minimal risk to participants' privacy:
(Alternative question phrasing: How do the risk(s) of this use of identifiable health information compare to the risks to privacy a person might reasonably experience in normal everyday life?)

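### No skin assessment is described after ICU transfer or withdrawal, so a late-found skin injury may be missed and the adverse-event count can only be biased downward

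*Combined protocol and SAP*

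**What the plan says.** All references are to the combined protocol and SAP.

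- **The harm.** Risks, Discomforts, Potential Harms and Monitoring, item 1: "The addition of a weighted blanket increases the amount of pressure placed on a patient's skin". Item 6 makes it a reportable event: "Adverse events are based on the risks identified above (patient skin injury or increased agitation", followed by two risks that do not concern the patient's body. Any adverse event leads the investigator to re-examine the protocol. Item 7 selects neither a monitoring board nor a monitoring plan.
- **Detection.** Item 5 of the same section withdraws a patient "if any skin changes are noted on daily physical examinations". Increased agitation and lack of assent are separate grounds for withdrawal.
- **End of enrolment.** Study Procedures, item 6: a patient stays in the study until withdrawn "or they are transferred from an ICU level of care".
- **Collection period and content.** HIPAA, item 2: "The following health information will be collected from the participant's medical record while enrolled in the study". The list that follows is medical history and diagnoses, "agitation and delirium scores, sedation and pain medications given and amounts given, hospital length of stay, ICU length of stay", and days ventilated.
- **Governing list.** Secondary Data/Specimen Details, item 1: "See attached Data Collection Spreadsheet document which contains all information that will be obtained from the EHR". The examples given there do not mention skin, but they are open-ended, and the spreadsheet itself is not in the text.

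**The concern.** Read together, these sections describe skin surveillance that stops when enrolment stops. Blankets are worn overnight, between 7pm and 7am. A patient transferred in the morning before that day's examination leaves the study with the last night's exposure unexamined. One-night patients are foreseen, because surveys go to anyone who used the blanket for at least one night. A patient withdrawn for agitation or lack of assent also leaves enrolment, possibly while still in the ICU.

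Two things depend on the count. First, with no monitoring board or plan, the trigger for re-examining the protocol works only if injuries are found and recorded. Second, the results are meant to support a larger randomised trial (Background, Rationale and Goals, item 4), and Project Details, item 1 classes the work as a device safety or effectiveness evaluation. A low or zero injury count is therefore likely to be carried forward as reassurance about safety.

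**Working it through.** **1. What the plan gives.** The denominator is 25 + 25 = 50 patients (Study Population, item 3). The plan states no expected injury rate, tolerability threshold, examination time, transfer time or length of stay. It has no figure of its own to reproduce on this point.

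**2. Where an injury is first seen, and what the text provides.**

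| First seen | Ascertainment described |
|---|---|
| Still enrolled, in ICU | Daily examination; withdrawal; named adverse event |
| After transfer from ICU-level care | None described |
| After withdrawal for another reason | None described |

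The gap is the last two rows only. An injury seen the morning after a blanket night, in a patient still enrolled, is covered.

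**3. Direction.** Let p be the true injury risk per patient and f the share of injuries first seen after the window and not captured. The counted risk is p(1 − f), which cannot exceed p. If f = 0 there is no bias.

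**4. Precision of a zero count, with full capture.** The one-sided 95% upper limit for 0 of n is 1 − 0.05^(1/n).
- n = 50: 1 − 0.05^(1/50) = 5.8%
- n = 25 (one site): 1 − 0.05^(1/25) = 11.3%

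These limits bound p(1 − f), not p. If f were 25%, the limit on p from 0 of 50 would be 5.8% / 0.75 = about 7.8%. If f were 50%, it would be 5.8% / 0.50 = about 11.6%.

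**5. Illustration on assumed values.** The documents give neither p nor f, so I take p from 2% to 10% and f from 0% to 50%. The chance of counting no injuries in 50 patients is (1 − p(1 − f))^50.

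| p | f = 0% | f = 25% | f = 50% |
|---|---|---|---|
| 2% | 36.4% | 47.0% | 60.5% |
| 5% | 7.7% | 14.8% | 28.2% |
| 10% | 0.5% | 2.0% | 7.7% |

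At p = 5%, the expected number missed is 50 × 0.05 × f, or about 0.6 at f = 25% and 1.25 at f = 50%. These figures show how sensitive a zero count is to f. They do not estimate the undercount in this study.

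**The case against.** The strongest reply is that the governing list is unseen and the plan states no cut-off for adverse events. The spreadsheet is said to hold everything taken from the EHR, and the HIPAA entry answers a request for a summary. Adverse events are defined by type, with no time limit. The collection wording is not strictly applied either: hospital length of stay is on the list and cannot be known when a patient leaves the ICU for a ward. The Secondary Data section also mentions removal from the study and completion of data collection as two separate steps. Finally, eligibility screening considers skin, so some reference state exists.

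Most of this stands, and it rules out several stronger readings that a reader might infer:

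- *Late-found injuries are excluded by rule.* No rule says so. The capture period is unstated.
- *Skin is not collected.* Only the visible summaries omit it.
- *A tolerability endpoint is biased.* None is defined. The result affected is the adverse-event count.
- *Between 20% and 100% of exposure is unobserved.* That is 1/k for stays of five nights down to one, assuming the final night is never examined. It is a worst-case share of nights, not of injuries missed.
- *The site with shorter stays is affected more.* The documents give no length-of-stay figures for either site.

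The reply does not close the gap. A skin field in the spreadsheet would still be subject to the collection period written in the HIPAA section, and no section describes looking for skin injury after transfer or withdrawal. Screening excludes some skin injuries but admits patients with injuries on areas easily left uncovered, and no recorded baseline is described against which a later change could be judged.

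**Conclusion.** The point holds as a gap in ascertainment. The text supports three statements: enrolment, and with it the written collection period, ends at withdrawal or ICU transfer; no later skin check is described; and any injury missed for that reason can only lower the count. It does not support saying that such injuries will be missed, or how many. The size is unknown, and is zero if no injury surfaces late or if late injuries are captured by a route not shown. The 5.8% upper limit for 0 of 50 assumes complete capture within the stated window and says nothing about injuries first seen outside it. The plan should be changed, because skin injury is the physical harm from blanket pressure that the protocol itself names.

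**What to change.** 1. Confirm that the data spreadsheet includes charted skin assessments, or add them: the last charted before first blanket use, each one during enrolment, and the first charted after final blanket removal, including on the receiving ward or after withdrawal for another reason.
2. Amend the collection-period wording in HIPAA, item 2, and the authorization to match. This needs reconciling anyway, because hospital length of stay is already collected.
3. Report skin injuries over all patients with any blanket exposure, with the capture window stated, an exact confidence interval, and the number of exposed patients who have no charted assessment after removal.

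**Cost.** Modest extra abstraction of existing charting from an EHR common to both sites, and a wording change to the authorization. It asks for no new examination. The Review Setup page carries a continuing-review category in which only data analysis remains, so abstraction may have to be retrospective and would need IRB approval. The linkage key is kept until IRB closure, which should make this possible. The change must also be squared with the undertaking in the Secondary Data section not to re-identify patients once data collection is complete. If abstraction is not feasible, the capture window should at least be stated beside any injury count.
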